#### **6.2.1.1.1 Immune-related RECIST (irRECIST)**

Immunotherapeutic agents may produce anti-tumor effects by potentiating endogenous cancer-specific immune responses. The response patterns seen with such an approach may extend beyond the typical time course of responses seen with cytotoxic agents and can manifest a clinical response after an initial increase in tumor burden or even the appearance of new lesions.

Conventional RECIST 1.1 may thus not provide a complete response assessment of immunotherapeutic agents. To account for the unique tumor response characteristics seen with treatment with immunotherapy, irRECIST 1.1 has been adapted from conventional RECIST [Nishino 2013] (Appendix 4).

Assessment of potential tumor progression is the responsibility of the Investigator. The Investigator will determine the date of progression and report it in the appropriate eCRF.

#### **6.2.1.1.2 Survival Follow-up**

Post-treatment tumor status in subjects whose disease has not progressed, and survival follow-up will be conducted until study completion. Subjects for whom disease progression has not been observed will have assessments of tumor status every 12 weeks ( $\pm 1$  week) until a date of disease progression is obtained, initiation of another anti-cancer treatment, or referral to hospice. Survival will be followed approximately every 12 ( $\pm 1$ ) weeks by telephone contact or e-mail for up to 12 months after the last dose of HBI-8000.

### **6.2.2 Safety Assessments**

The following safety evaluations will be performed at screening and various time points throughout the course of the study (treatment phase, post-treatment, etc., refer to Table 1):

- Medical history
- Physical examinations
- Evaluation of adverse events (AEs)
- ECOG performance status
- Vital signs
- Electrocardiogram (ECG)
- Clinical Safety Laboratory tests: complete blood count (CBC) and serum chemistry, Thyroid function (Baseline, Day 1 of each Cycle throughout study and EoT Safety Follow-Up Visit), hepatitis B and C panel (Screening), urinalysis (Baseline and EoT Safety Follow-up Visit), serum pregnancy test (at Baseline and during study when clinically indicated, if applicable)
- Coagulation tests to include PT/INR, aPTT (at Baseline, at EoT Safety Follow-Up Visit, and during the study when clinically indicated)

Treatment-emergent adverse events reported by the subjects or observed during physical examination, vital sign assessment, ECGs and/or review of laboratory test results will be assessed according to NCI CTCAE v.5.0 (CTCAE home page:

<http://evs.nci.nih.gov/ftp1/CTCAE/About.html> and recorded by severity grades and association

with HBI-8000 and pembrolizumab. Results of clinical laboratory tests, vital signs, physical findings, ECGs and ECOG performance status will be monitored and recorded.

### **6.2.2.1 Vital Signs, ECG, Physical Examinations, and ECOG Assessments**

Vital sign measurements will include temperature, heart rate, systolic blood pressure (SBP) and diastolic blood pressure (DBP) in a supine position. Vital sign measurements should be performed prior to the ECG and after the subject has been supine for at least 5 minutes.

Physical examinations will include the evaluation of head, eye, ear, nose, and throat (HEENT), cardiovascular, dermatological, musculoskeletal, respiratory, gastrointestinal, and neurological systems. Changes from baseline abnormalities should be recorded at each subsequent physical examination. New or worsened abnormalities should be recorded as adverse events if appropriate.

ECOG Performance Status will be used to assess subjects' performance status. Refer to [Appendix 1](#). for definitions of ECOG performance score.

### **6.2.2.2 Clinical Laboratory Assessments**

Hematology testing will include the following parameters: hemoglobin, hematocrit, red blood cell (RBC) count, WBC count with differential, and platelet count.

Coagulation will include the following parameters: prothrombin time (PT), activated partial thromboplastin time (aPTT), and International Normalized Ratio (INR).

Serum chemistry testing will include the following parameters: blood urea nitrogen (BUN), creatinine, AST, ALT, lactate dehydrogenase (LDH), total bilirubin (including direct fraction if total bilirubin is abnormal), lipase, amylase, thyroid stimulating hormone (TSH), free thyroxine (T4) (direct), total protein, albumin, uric acid, alkaline phosphatase, sodium, potassium, calcium, magnesium, phosphorus and glucose.

Urinalysis will be performed using a dipstick method followed by microscopic examination in the event of abnormal dipstick results.

[figure not shown]
Pregnancy test: All women of childbearing potential (including those who have had a tubal ligation) will have a serum pregnancy test at baseline and at the EoT Safety Follow-up visit.

Adverse Events and Serious Adverse Events: All abnormal laboratory results must be reviewed by the Investigator and evaluated. All clinically significant results will be documented as adverse events. Clinically significant is defined as an abnormal laboratory value that meets the following criteria:

- Requires additional tests, medication and/or interventions to follow or treat the event
- Results in subject discontinuation
- Results in an SAE
- Manifests clinically
- Changes the treatment regimen of the subject
- New onset of any  $\geq$ grade 3 event (regardless of relationship to study drug or outcome of the event)

### **6.2.2.3 PD-L1 Testing**

The PD-L1 status will be determined by PD-L1 IHC 22C3 pharmDx test (Dako North America, Inc) approved by FDA in 2015, performed at local diagnostic laboratory.

PD-L1 IHC 22C3 pharmDx is indicated as an aid in identifying NSCLC patients for treatment with KEYTRUDA® (pembrolizumab). 

### **6.2.2.4 Adverse Events**

An adverse event (AE) is any unfavorable and unintended sign (including an abnormal laboratory finding), symptom, or disease temporally associated with the use of a medical treatment or procedure that may or may not be considered related to the medical treatment or procedure. Assessment of the occurrence of an AE will be based on changes in the subject's physical examination, ECG, clinically significant laboratory results, and/or signs and symptoms. An AE also includes any newly occurring event or previous condition that has increased in severity or frequency after the subject received the first dose of Study Treatment.

Adverse events will be monitored until they are resolved and/or deemed stable, as in the case of an event that is related to a chronic condition or intercurrent illness. Medical care will be provided, as defined in the informed consent, for any AE related to study participation.

#### **6.2.2.4.1 Serious Adverse Events**

A serious adverse event (SAE) is any untoward medical occurrence, regardless of its relationship to Study Treatment, that meets any of the following criteria:

- Results in death
- Is life-threatening (i.e., the subject is at a risk of death at the time of the event; it does not refer to an event which hypothetically might have caused death if it were more severe)
- Requires in patient hospitalization or prolongation of existing hospitalization; hospital admissions and/or surgical operations planned before or during a study are not considered AEs if the illness or disease existed before the subject was enrolled in the study, provided that it did not deteriorate in an unexpected way during the study. (Please read the **NOTE** below)
- Results in persistent or significant disability/incapacity
- Is a congenital abnormality/birth defect
- Is an important medical event, defined as a medical event that may not be immediately life-threatening or result in death or hospitalization, but based upon appropriate medical

and scientific judgment, may jeopardize the subject or may require intervention (e.g., medical or surgical) to prevent one of the other serious outcomes listed in the definition of an SAE. Examples of such events include, but are not limited to, intensive treatment in an emergency room or at home for allergic bronchospasm; blood dyscrasias or convulsions that do not result in hospitalization.

It is common that several other AEs are observed when the SAE qualifying event occurs. Not all observed AEs are SAEs. Efforts must be made to identify the chief event(s) leading to the SAE qualifying event, e.g., hospitalization.

Suspected transmission of an infectious agent (e.g., pathogenic or nonpathogenic) via the study drug is an SAE.

Any component of a study endpoint that is considered related to study therapy (e.g., death is an endpoint) if death occurred due to anaphylaxis, anaphylaxis must be reported.

Although pregnancy and overdose are not always serious by regulatory definition, these events must be reported on a Pregnancy Surveillance form and an AE/SAE form respectively in the eCRF within 24 hours of Investigator awareness of the overdose, regardless of association with an AE.

Pregnancies of study subject or partner of study subject receiving Study Treatment currently or within 28 days of last dose, regardless of outcome.

If only limited information is initially available, follow-up reports are required. (Note: Follow-up SAE reports should include the same Investigator term(s) initially reported, change in event terms should be accompanied by proper documentation of the rationale for the event term change.). Multiple signs, symptoms and manifestation of disease entity should be subsumed under umbrella diagnosis rather than reporting the signs and the symptoms of the diagnosis.

If an ongoing SAE changes in its intensity or relationship to Study Treatment or if new information becomes available, a follow-up SAE report should be sent within 24 hours to the Sponsor (or designee) using the same procedure used for transmitting the initial SAE report.

All SAEs should be followed to resolution or stabilization

**NOTE:** The following hospitalizations are not considered SAEs in sponsored clinical studies:

- A <24-hour visit to the emergency room or other hospital department, that does not result in admission (unless considered to be an important medical event or an event that is life threatening)
- Elective surgery planned prior to signing ICF
- Admissions as per protocol for a planned medical/surgical procedure
- Routine health assessment requiring admission for pretreatment assessment/trending of health status (e.g., routine colonoscopy)
- Medical/surgical admission for a purpose other than remedying ill state of health and was planned prior to entry into the study. Appropriate documentation is required in all these cases.

- Admission for a life circumstance that has no bearing on health status and requires no medical/surgical intervention (e.g., lack of housing, economic inadequacy, caregiver respite, family circumstances, administrative)
- Admission for progressive disease (PD)

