### 7.5.2.1 Adverse Events

Adverse events will be coded using the MedDRA classification system version 24.0 or higher. The severity of the events will be graded by the Investigator according to the NCI CTCAE version 5.0 or higher.

All adverse events (AEs) will be summarized, and emphasis will be placed on treatment-emergent adverse events (TEAEs). An AE will be considered treatment-emergent if it occurs or worsens in severity from pre-treatment state on or after the first dose date of any study treatment through 30 days after the last dose of any study treatment. All AEs will be listed.

An overall summary of AE will be provided by the frequency and percentage of subjects experiencing an AEs by MedDRA systems organ class (SOC) and preferred term (PT). TEAEs will be summarized by the frequency and percentage of subjects experiencing TEAEs SOC and

PT, and by worst NCI CTCAE severity grade. Summaries will also be provided for treatment related TEAEs, namely, those judged by the Investigator to be at least possibly related to study drug treatment.

Adverse events resulting in discontinuation from treatment or withdrawal from the study, Grade 3 or higher, serious adverse events, and deaths on-study will be tabulated.

All AEs noted during the study will be listed per subject, detailing reported term, system organ class, preferred term, start date, stop date, severity, relationship to each Treatment, TEAE flag, and outcome.

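### The exemption for planned admissions in the SAE definition is looser than the AE, TEAE and NOTE wording, so an expected worsening with an admission arranged on study can lose SAE status

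*Combined protocol and SAP*

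**What the plan says.** The hospitalization criterion in Section 6.2.2.4.1 carries an exemption. On admissions and operations it reads: "planned before or during a study are not considered AEs if the illness or disease existed before the subject was enrolled in the study". One limit is set on this, concerning the illness: "provided that it did not deteriorate in an unexpected way during the study". The bullet then sends the reader to a NOTE at the end of the section.

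That NOTE lists hospitalizations that are not SAEs. Two of its items cover similar ground to the bullet. One is "Elective surgery planned prior to signing ICF". The other is "Medical/surgical admission for a purpose other than remedying ill state of health and was planned prior to entry into the study".

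The general AE definition in Section 6.2.2.4 includes any "previous condition that has increased in severity or frequency after the subject received the first dose of Study Treatment". For the analysis, Section 7.5.2.1 states: "An AE will be considered treatment-emergent if it occurs or worsens in severity from pre-treatment state", within a window from first dose to 30 days after last dose. Neither definition asks whether the worsening was expected.

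**The concern.** The bullet differs from the neighbouring text in three ways.

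- **Timing.** It exempts admissions planned during the study as well as before it. The two comparable NOTE items stop at consent or study entry.
- **Threshold.** It withdraws the exemption only for unexpected deterioration, so expected deterioration stays exempt. The AE and TEAE definitions have no such qualifier.
- **Status.** It removes AE status. The NOTE removes only SAE status.

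Safety and tolerability is a secondary objective (Section 2.2) in a non-randomized study (Section 3.1), so SAE rates will be read without a comparator. Section 1.1.3.3 reports anemia in 42.7%, dyspnea in 37.1% and peripheral edema in 33.7% of patients given HBI-8000 with nivolumab. Eligibility admits some related baseline conditions: hemoglobin from 9.0 g/dL (Section 4.1), and recurrent effusion with an indwelling port and heart failure below NYHA III (Section 4.2). In such subjects a worsening is easily called expected for the prior illness, and a drug effect is hard to separate from it. SAE classification also starts the 24-hour report (Section 6.2.2.4.5) and feeds the sponsor safety committee's review (Section 6.3).

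**Working it through.** **1. The plan's own figure.** Table 4 is the only design figure that depends on AE counts. With P(at least one) = 1 − (1 − p)^n and p = 10%:

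- n = 20: 1 − 0.9^20 = 87.8%
- n = 24: 1 − 0.9^24 = 92.0%

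Both match Section 7.1. They concern whether an AE is seen at all, not whether it is classed as serious, so loss of SAE status alone does not change them.

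**2. The rules side by side.**

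| Text | Time limit on planning | What worsening counts | Status removed |
|---|---|---|---|
| 6.2.2.4.1, hospitalization bullet | Before or during study | Only unexpected deterioration | AE |
| 6.2.2.4.1, NOTE, elective surgery | Before consent | Not addressed | SAE |
| 6.2.2.4.1, NOTE, other medical/surgical admission | Before entry, and not to remedy ill health | Not addressed | SAE |
| 6.2.2.4, AE definition | None | Any rise in severity or frequency after first dose | None |
| 7.5.2.1, TEAE definition | None | Any rise in severity from pre-treatment | None |

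**3. One case put through each rule.** Take a subject whose illness pre-dates enrollment. It worsens after first dose as the Investigator expected, an admission is arranged on study to treat it, and no other seriousness criterion is met.

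- Section 6.2.2.4: AE. Section 7.5.2.1: treatment-emergent, if severity rose.
- Hospitalization criterion without the exemption: SAE.
- Hospitalization bullet as written: the admission is exempt, so the event is not an SAE on this criterion.
- The two NOTE items: not exempt, because the admission was planned after entry and is meant to remedy ill health.

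Two sites following different parts of one section can therefore report the same event differently. If the deterioration was unexpected, the bullet's exemption no longer applies.

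**4. Whether other sections close the gap.**

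- Section 6.2.2.4.4: a procedure is not an AE, but the condition behind it must be reported. This addresses procedures rather than medical admissions, and does not say whether the condition is serious.
- Section 6.2.2.4.11: significant worsening is recorded as a nonserious or serious AE, as appropriate. This supports AE recording but does not restore the hospitalization criterion.
- Sections 6.2.2.2 and 6.2.2.4.7: clinically significant laboratory changes are AEs, which covers most worsening anemia.
- Section 6.2.2.4.5: doubtful seriousness requires an SAE report. A site reading the bullet literally has no doubt, because it is told the admission is not an AE.

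AE recording is thus largely protected. SAE status on the hospitalization criterion is not.

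**5. Size.** One subject moved out of the SAE table changes the rate by 1/24 = 4.2 points or 1/20 = 5.0 points. The documents do not say how many subjects would be affected. Assuming none, one or two, the fall is 0, 4.2 or 8.3 points at n = 24, and 0, 5.0 or 10.0 points at n = 20.

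**The case against.** The strongest reply is that the bullet exempts the admission or operation, not the worsened illness. It sits inside one seriousness criterion, and nothing says that it overrides the AE or TEAE definitions. A reader might infer that real worsening drops out of both the AE and SAE counts and pulls down the Grade 3 or higher rates. The documents do not support that reading. Loss from the AE count requires the bullet to override Sections 6.2.2.4, 6.2.2.4.4 and 6.2.2.4.11. CTCAE grading (Sections 6.2.2.4.2 and 7.5.2.1) attaches to the condition, so exempting an admission does not change a grade. This part of the objection stands.

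The exposure is also narrow. The admission must be planned, the illness pre-existing and the deterioration not unexpected, so unplanned admissions fall outside the exemption. Death, life-threatening events, disability and important medical events remain serious. Section 4.2 excludes many subjects with serious cardiac or lung disease. These points also stand.

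The conflict with the NOTE is partial. Several NOTE items have no pre-consent limit, including per-protocol procedures, routine health assessments, life-circumstance admissions and admission for progressive disease. None of them squarely covers an admission to treat worsening of a prior illness, so the conflict remains for the case above.

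What the objection does not answer is SAE status. Even with the condition recorded as an AE, the bullet removes the criterion that would have made it serious.

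**Conclusion.** The conflict is real and should be corrected. Followed literally, an expected worsening of a prior illness with an admission arranged on study can lose SAE status on the hospitalization criterion and escape 24-hour reporting. AE recording of the same event may be inconsistent between sites. This rests on a site applying the bullet as written and on no other seriousness criterion being met.

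The effect is confined to SAE classification and reporting. In most cases the worsened condition is still an AE, its grade is unchanged, and the primary ORR analysis is untouched. The documents contain no figure from which an undercount could be estimated. The per-subject shift of 4.2 to 5.0 points shows only how sensitive a rate is in 20 to 24 subjects. It is not evidence that the reported SAE rate will be biased by any given amount.

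**What to change.** Amend Section 6.2.2.4.1 in four places.

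1. Make the bullet remove SAE status rather than AE status, matching the NOTE.
2. Replace the proviso on unexpected deterioration with a condition that the illness did not increase in severity or frequency after informed consent. Consent is the right anchor because SAEs are collected from consent (Section 6.2.2.4.5). Anchoring at first dose would exempt a pre-planned admission for a condition that worsened between consent and first dose.
3. Use one time reference for planning in the bullet and the NOTE, so that an admission arranged on study is exempt only when the condition has not worsened. Simply deleting the words on planning during the study would remove the exemption for elective admissions for stable conditions.
4. State that worsening of the underlying condition after first dose is always recorded as an AE and assessed for seriousness.

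The cost is a short wording amendment, a matching update to the eCRF completion guideline, a few more SAE forms and possibly a slightly higher reported SAE rate.

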Diagnosis and main criteria for inclusion:	
Inclusion Criteria
 
Subjects may be entered in the study only if they meet all the following criteria:
 
 
1. Adults at least 18 years of age.
 
2. Eastern Cooperative Oncology Group (ECOG) performance status <math>\leq 2</math>.
 
3. Histopathologically confirmed diagnosis of NSCLC PD-L1 expression TPS <math>\geq 1\%</math> as determined by an FDA-approved test.
 
4. Have at least one measurable target lesion as defined by RECIST v.1.1.
 
5. Have not received immune checkpoint inhibitor therapy or more than one regimen of chemotherapy for advanced or metastatic disease. Subjects who have previously received immune checkpoint inhibitor therapy in the adjuvant or neoadjuvant setting may be allowed if disease progression occurred <math>>6</math> months after the last dose and no clinically significant immune related toxicities leading to treatment discontinuation were observed.
 
6. Prior adjuvant or neoadjuvant systemic therapy with chemotherapy, EGFR or ALK mutation directed therapy must have been completed <math>>4</math> weeks before Cycle 1 Day 1 (C1D1) dosing and recovered from all treatment related toxicity.
 
7. Any prior palliative radiotherapy or minor surgery must be completed at least 2 weeks and 1 week respectively before C1D1 dosing and recovered from all treatment related toxicities.
 
8. Adequate major organ functions at baseline as evidenced by laboratory findings within 14 days prior to C1D1 study drug administration as defined below: 
 
a. White blood cells (WBC) <math>\geq 3000/\mu\text{L}</math>, neutrophils <math>\geq 1500/\mu\text{L}</math>, platelets <math>\geq 100 \times 10^3/\mu\text{L}</math>, hemoglobin <math>\geq 9.0 \text{ g/dL}</math>, independent of transfusion.
 
b. Serum creatinine <math>\leq 1.5 \text{ mg/dL}</math>, normal electrolytes, phosphorus, and calcium.
 
c. Aspartate aminotransferase (AST) and alanine aminotransferase (ALT) <math>\leq 3 \times</math> upper limit of normal (ULN), alkaline phosphatase <math>\leq 2.5 \times</math> ULN unless bone metastases present, bilirubin <math>\leq 1.5 \times</math> ULN (unless known Gilbert's disease where it must be <math>\leq 3 \times</math> ULN) and serum albumin <math>\geq 3.0 \text{ g/dL}</math>.
 
d. Thyroid stimulating hormone (TSH) within normal limits.
 
 
 
9. Life expectancy <math>\geq 12</math> weeks.
 
10. A negative serum pregnancy test at baseline for women of childbearing potential (WOCBP).
 
11. Women of childbearing potential. (WOCBP), non-surgically sterile or premenopausal female capable of becoming pregnant and men (due to potential risk of drug exposure through the ejaculate) must agree to use an acceptable method of contraception while enrolled on this study, and for a period of 5 months following the last dose of treatment. Acceptable methods of birth control in this trial include 2 highly effective methods of birth control (as determined by the Investigator; one of the methods must be a barrier technique) or abstinence.
 
12. Have the ability to understand and the willingness to sign a written informed consent document.
 
 
Exclusion Criteria
 
Subjects who fulfill any of the following criteria at screening will not be eligible for admission into the study:
 
 
1. History of Grade <math>\geq 3</math> hypersensitivity reactions to monoclonal antibodies.
 

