### **3.1.1      Expected Duration of Subject Participation**

Subject participation duration from screening through end of treatment visit is approximately up to 38 months, including:

Screening period:	Up to 28 days
Treatment period:	Until radiographic disease progression per RECIST v1.1 (assessed by the Investigator), unacceptable toxicity, or other reasons for discontinuation with a maximum treatment duration of 24 months, unless there is an agreement between the Sponsor and the Investigator to allow HBI-8000 beyond 24 months.
Short-term Follow up/ End of treatment (EoT) period	Up to 30 days ( $\pm 3$ days) after the last dose HBI-8000. This will be defined as EoT.
Long-term Follow-up period:	Every 12 weeks (3 months) up to a maximum of 12 months after the last dose of HBI-8000.

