## **3.3      End of Treatment Definition**

The end of treatment is defined as the date of the last dose of HBI-8000 taken by the subject.

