11. Females of childbearing potential (non-surgically sterile or premenopausal female capable of becoming pregnant) and all males (due to potential risk of drug exposure through the ejaculate) must agree to use an acceptable method of contraception while enrolled on this study and for 5 months after the last dose of study drug. Acceptable methods of birth control in this trial include 2 highly effective methods of birth control (as determined by the Investigator; one of the methods must be a barrier technique) or abstinence.
12. Have the ability to understand and the willingness to sign a written informed consent document.

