#### **6.1.4 End of Treatment (EoT) Safety Visit Assessments**

The EoT safety follow-up visit will be conducted 30 ( $\pm 3$ ) days following the last dose of HBI-8000, or before the initiation of new cancer treatment, whichever is earlier. Assessments will include a physical examination, vital signs, ECOG performance status, weight, concomitant medications, laboratory tests (hematology, chemistry, coagulation and urinalysis), serum pregnancy test (if applicable), ECG, and assessment of any ongoing adverse events.

Subjects with HBI-8000-related AEs of Grade  $\geq 2$  observed at the EoT visit should be followed-up and assessed monthly until the AEs have resolved to Grade  $\leq 1$  or are determined to be chronic or subject receives other anti-cancer therapy.

Any pregnancies while on this study or within 28 days of the last dose of HBI-8000 will be followed up, with female subject's permission, until the birth of the baby (Refer to Section [6.2.2.4.8](#)).

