#### **6.2.2.4.8 Pregnancy**

If a pregnancy is reported during active treatment of HBI-8000 until EoT, the Investigator must inform the Sponsor within 24 hours of learning of the pregnancy. Protocol-required procedures for study discontinuation and follow-up must be performed on the subject unless contraindicated by pregnancy. Other appropriate pregnancy follow-up procedures should be considered if indicated.

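### Contraception is required for 5 months after the last dose, but the stated pregnancy-reporting limits end at about day 28 to 33, and EoT, which sets one of those limits, is defined in two ways

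*Combined protocol and SAP*

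**What the plan says.** **Contraception.** Inclusion criterion 11 applies to women of childbearing potential and to men, the latter because of possible drug exposure through the ejaculate. The Synopsis sets it "for a period of 5 months following the last dose of treatment". Section 4.1 requires "contraception while enrolled on this study and for 5 months after the last dose of study drug".

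**Reporting.** Section 6.2.2.4.1 says that pregnancy must be reported within 24 hours, although the sentence, which also covers overdose, ties the clock to awareness of the overdose. A separate line then reads "Pregnancies of study subject or partner of study subject receiving Study Treatment currently or within 28 days of last dose, regardless of outcome". This is the only rule that names partners. Section 6.2.2.4.8 adds: "If a pregnancy is reported during active treatment of HBI-8000 until EoT, the Investigator must inform the Sponsor within 24 hours". Section 6.2.2.4.5 has pregnancy information in its heading, but its text gives no pregnancy window.

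**Follow-up.** Section 6.1.4 states: "Any pregnancies while on this study or within 28 days of the last dose of HBI-8000 will be followed up". That follow-up needs the female subject's permission and runs to the birth. Partners are not mentioned.

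**EoT.** Section 3.3: "The end of treatment is defined as the date of the last dose of HBI-8000 taken by the subject". Section 3.1.1 describes a period of up to 30 ± 3 days "after the last dose HBI-8000. This will be defined as EoT". The EoT visit can also be brought forward, because Section 6.1.4 places it 30 ± 3 "days following the last dose of HBI-8000, or before the initiation of new cancer treatment, whichever is earlier".

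**The concern.** The protocol asks subjects to avoid conception for 5 months but obliges sites to report a conception for only about the first month of that period. A site that follows the stated limits need not tell the Sponsor of a partner's pregnancy, or of one in a subject who has left the study, in roughly months 2 to 5. That the 5 months reflects a possible risk to the fetus is an inference. The documents give a reason only for including men.

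Other provisions do not clearly close the gap. The last scheduled pregnancy test is at the EoT visit (Table 1 footnote m, Section 6.2.2.2). Section 6.2.2 allows later tests when clinically indicated, but that is not a reporting rule. The 90-day extended collection in Section 6.2.2.4.6 names SAEs and immune-related events of special interest, not pregnancy.

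The duplicate EoT definition is a drafting error in its own right, because the limit in Section 6.2.2.4.8 is expressed only through that term.

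What is at stake is completeness of safety information, not ORR, any other efficacy estimate, or the sample size.

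**Working it through.** The plan gives no figure to reproduce. The check compares calendar windows, with day 0 as the last dose and the same last dose assumed for both clocks.

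**Inputs**
- Contraception: 5 calendar months (Synopsis and Section 4.1, criterion 11), which is 150 to 153 days depending on the starting month.
- Rule A, Section 6.2.2.4.1: to day 28, subject or partner.
- Rule B, Section 6.2.2.4.8: to EoT. This is day 27 to 33 if EoT is the visit at 30 ± 3 days, day 0 if EoT is the last-dose date, and in between if the visit is brought forward before new cancer treatment.

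**Step 1: rule A alone.** Uncovered days = contraception days − 28.
- 150 − 28 = 122 (122/150 = 81.3%)
- 153 − 28 = 125 (125/153 = 81.7%)

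**Step 2: rules A and B together.** Both are in force, so reporting runs to the later of day 28 and EoT.

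| Meaning of EoT in rule B | Reporting runs to | Uncovered days |
|---|---|---|
| Visit at day 27 to 33 | day 28 to 33 | 150 − 33 = 117 (78.0%) to 153 − 28 = 125 (81.7%) |
| Last-dose date (day 0) | day 28 | 122 to 125 |
| Visit brought forward before day 28 | day 28 | 122 to 125 |

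The combined gap is therefore 117 to 125 days on any meaning of EoT. Rule A is the only rule that names partners. If rule B is confined to subjects, the partner gap is 122 to 125 days.

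**Step 3: would the SAE window close it?** Even if the 90-day collection were applied to pregnancy, 150 − 90 = 60 to 153 − 90 = 63 days would remain.

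**Step 4: do the planned contacts reach the end of the 5 months?** Table 1 footnote s schedules them every 12 ± 1 weeks (84 ± 7 days) after the EoT visit.
- First contact: 30 + 84 = day 114 (27 + 77 = 104 to 33 + 91 = 124).
- Second contact: 30 + 2 × 84 = day 198 (27 + 2 × 77 = 181 to 33 + 2 × 91 = 215).

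The second contact falls after day 153 even at its earliest, so two existing contacts span the period when the clock starts at the last HBI-8000 dose.

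The results are calendar days without an explicit duty, not expected numbers of pregnancies.

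**The case against.** **The windows need not match.** A precautionary contraception period and a shorter mandatory reporting period can coexist, and nothing in the documents says that they must be equal. This stands, so alignment is a recommendation. Only the duplicate EoT definition is wrong as written.

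**The 28-day line may not be a limit.** Section 6.2.2.4.1 first says that pregnancy must be reported, without an end date. The 28-day line has no verb, and may be a list item or text broken in extraction. Reading it as the limit is natural but not the only reading, and the size of the gap depends on it.

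**Section 6.1.4 may cover much of the gap.** Section 4.4.1 treats the time after HBI-8000 stops as part of study participation, and subjects are followed for up to 12 months after the last dose. On that reading, pregnancies in female subjects still in follow-up would be followed, and the 28-day clause would still serve subjects who leave. This is plausible. However, the clause concerns follow-up rather than notification, and it does not name partners.

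**Two stronger readings are tempting.** A reader might infer that, if EoT is the last-dose date, the whole contraception period (150 to 153 days, 100%) has no reporting duty. The documents do not support that, because Section 6.2.2.4.1 still reaches day 28. The visit reading of EoT is also the better fit in Section 6.2.2.4.8, where an end at the last dose would add nothing to the words about active treatment. A reader might also infer that no drug is named for the pregnancy clock. Sections 6.1.4 and 6.2.2.4.8 both name HBI-8000. The looser wording is in the contraception criterion, which says only treatment (Synopsis) or study drug (Section 4.1).

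**Conclusion.** The concern holds in a limited form. Taken together, the stated reporting rules leave about 117 to 125 of the 150 to 153 contraception days (roughly 78 to 82%) with no explicit duty to report. This rests on reading the 28-day line in Section 6.2.2.4.1 as a limit, and on both clocks starting at the same last dose. If Section 6.1.4 extends to subjects in follow-up, the remaining gap is mainly partners and subjects who have left the study.

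It would go too far to conclude that every pregnancy after the first month goes unrecorded, or that the protocol breaches a rule of its own on matching windows. The point is low priority (COULD): few events are expected in 20 to 24 subjects, and no efficacy result or sample size changes. It is worth acting on because the remedy is cheap and concerns patient safety.

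**What to change.** 1. State one rule in Section 6.2.2.4.5 and cross-refer to it from Sections 6.1.4, 6.2.2.4.1 and 6.2.2.4.8. Any pregnancy in a subject or partner, from first dose through 5 months after the last dose, is reported within 24 hours of awareness of the pregnancy and followed to outcome, with the permission of the subject or pregnant partner.
2. Name the drug whose last dose starts the contraception clock, and use the same anchor for reporting.
3. Use one EoT definition in Sections 3.1.1 and 3.3. If the visit is meant in Section 6.2.2.4.8, say so.
4. Ask about pregnancy at the planned 12-weekly contacts until the 5 months end. With an HBI-8000 clock the first two contacts, at about days 114 and 198, are enough. A clock tied to a later pembrolizumab dose could need further contacts.
5. If a shorter reporting window is intended, state the reason.

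The cost is protocol wording, a longer reporting period and one added question at contacts already planned. No extra visits or tests are needed with an HBI-8000 clock.
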